4.4.7 VISIT 6, 3 MONTH FOLLOW UP VISIT AND EXIT

Participant to attend visit after 2 hours or more of MiSight study lens wear.

1. Collect unused study CLs;
2. Changes in medical history/medications;
3. Compliance with # of CL wear days/hours per day

4. Presenting VA

8. Spherical over-refraction

9. Slit lamp biomicroscopy

10. Questionnaires (CLIQ, QoV)

11. Lens removal

12. Biomicroscopy examination

14. Exit visual acuity with habitual correction

4.4.8 STUDY EXIT

The study exit form will be completed when a participant exits the study. This form will be completed either at study completion, or if the participant is discontinued from the study at another time. A study exit form must be completed for all participants who have taken a study ID number. If in the opinion of the investigator post-study follow-up visits are required, the exit form will be completed after the last follow-up visit.

Exit monocular and binocular distance vision will be recorded with either the participant's spectacles, refraction or habitual contact lenses. An exit biomicroscopy assessment will be conducted if not already completed on the same day for a concurrent study visit.

After the exit assessments have been completed, the participant and investigator will complete the study completion and remuneration forms. At this time the participant will be considered as having exited the study.

4.4.9 UNSCHEDULED VISITS

An unscheduled visit is defined as an interim visit requested by the participant or investigator due to an unanticipated problem. Data recorded at these visits will be entered into the database.

Only relevant and applicable unscheduled visit information will be included in the final report as deemed necessary by the lead investigator.

4.5 STUDY PROCEDURES

Table 3 summarizes the procedures at each visit. The order of procedures is described in sections 4.4.2 to 4.4.7.

Table 3: Summary of procedures to be conducted at scheduled visits

Procedures / Data	Screen & BL/Dispensing (75/90mins)	DV++ (30min)	2W (2W from DV) (60mins)	1M (1M from LD) (75mins)	2M (2M from DV) (15mins)	3M (3M from DV)(90mins) Final Visit	Unscheduled/ Adverse Events
Visit window	N/A	≤10 days from BL	± 4 days	+ 5 days - 5 days	+ 7 days - 7days	+ 7 days - 7 days	N/A
Informed consent	✓	-	-	-	-	-	-
Meet inclusion / exclusion criteria	✓	✓	-	-	-	-	-
Demographics	✓	-	-	-	-	-	-
Presenting VA	✓	✓	✓	✓	-	✓	✓
History at baseline	✓	-	-	-	-	-	-
History since last visit, including updated medical problems / previous events / treatment	-	✓	✓	✓	-	✓	✓
Auto-refraction + keratometry	✓	-	-	-	-	-	-
Subjective refraction + VA	✓	-	-	-	-	✓	*
██████████		✓				✓	
██████████	✓	-	✓	✓	-	✓	-
██████████	✓	-	-	-	-	✓	-
██████████	✓	-	-	✓	-	✓	-

	✓	-	-	✓	-	✓	-
Spherical Over-refraction + VA	-	-	✓	-	-	✓	-
Wear time review	-	-	✓	✓	✓	✓	*
Compliance assessment / Lens and solution returns	-	-	✓	✓	-	✓	*
Slit-lamp biomicroscopy: Assessment of lenses worn at visit and ocular assessment	✓	✓	✓	✓	-	✓	✓
Questionnaires (including QOL/OOV questionnaires)	***	+	✓	✓	✓	✓	-
Photos / video	*	*	*	*	-	*	*
Adverse event assessment	✓	✓	✓	✓	-	✓	✓
Visit summary	✓	✓	✓	✓	-	✓	✓
*	At investigators' discretion						
**	If visual acuity (VA) is decreased by 2 lines or more from BL or LD						
***	With habitual lenses						
+	If lenses dispensed						

4.5.1 CASE HISTORY

Demographics:

Demographic information from the participant will be obtained, including age and sex.

Medical History:

At screening, information will be obtained from participants about the current medication, allergies, and any medical conditions. At visits 2 (if applicable), 3, 4 and 6 participants will be asked about changes in their medication or health.

Contact Lens History:

Information will be obtained from the participant about the current contact lens type (lens name, brand), lens power and use of artificial tears. Participants will be asked their typical lens wear time (hours/day and days/week).

4.5.2 QUALITY OF LIFE (CLIQ) AND QUALITY OF VISION QUESTIONNAIRES (QOV):

Participants will be asked to complete questionnaires based on the time period of contact lens wear specified in the questionnaire.

4.5.3 VISUAL ACUITY

Visual acuity for distance will be measured using high contrast computer-generated acuity charts in high illumination. Participants will be asked to read letters that progressively decrease in size on a computer screen located at a distance of 6 meters.

4.5.4 AUTOREFRACTION

Participants will be asked to focus on a target while seated at an instrument that measures their approximate spectacle prescription and corneal shape.

4.5.5 SUBJECTIVE REFRACTION

Participants will be asked to read a letter chart from a distance through lenses placed in front of their eyes. They will also be asked to compare clarity of their vision between different lenses placed in front of their eyes. This procedure aids to determine their spectacle and/or contact lens prescription.

4.5.6 SLIT LAMP BIOMICROSCOPY

The participant will be seated behind a slit lamp and the following may be assessed at any visit:

External adnexa anomalies:

Any observations of the anterior eye (e.g. pterygium, pinguecula, etc) will be recorded.

Cornea:

Any corneal observations (such as infiltrates, old scars, etc) will be documented.

Conjunctival redness:

Ocular redness will be assessed for the bulbar and limbal conjunctiva using the EFRON grading scale (0 to 4, 0 = normal; 0.1 increments).

Corneal and conjunctival staining with fluorescein:

Corneal staining will be assessed for 5 zones, by grading type (0-4, 0.5 steps), extent (0-4, 0.5 steps) and depth (0-4, integer steps);

Lens edge related conjunctival staining and conjunctival indentation will be assessed for 4 zones (0-4, 0.5 steps).

Palpebral conjunctival hyperemia and roughness:

The redness and roughness of the upper and lower eyelids (tarsal plate zone 2) will be assessed using the Efron grading scale (0 to 4, 0 = normal/ uniform satin appearance; 0.25 steps).

4.5.7 CONTACT LENS FIT

Contact lens fit:

Lens fit will be assessed to ensure acceptable lens fit with study lenses at the screening visit.

At V2 and V3, lens centration and movement will be assessed as follows

- *Lens centration (scale: optimal, slight decentration, moderate decentration but not encroaching limbus, excessive & occasionally encroaching limbus);*
- *Lens movement for primary gaze (-2 = Unacceptably tight; -1 = Slightly tight but acceptable; 0 = Optimal; +1 = Slightly loose but acceptable; +2 = Unacceptably loose); lens tightness on push-up test (0-100 scale, with 50 being optimal; 5-point steps).*

[REDACTED]

[REDACTED]

[REDACTED]

[REDACTED]

[REDACTED]

[REDACTED]

5 MONITORING PROTOCOL ADHERENCE

All personnel involved in this study will be listed on a delegation log and their training will be documented. Consent documentation will be reviewed by personnel not involved in the consent process. Visit windows will be reviewed when determining the analysis cohort. All protocol deviations will be reviewed by the Lead Investigator. Suspected major protocol deviations will be reviewed by the Principal Investigator and reported to the sponsor and the University of Waterloo's Office of Research Ethics (ORE) within 7 days of becoming aware of them (as per ORE's guidelines).

6 POTENTIAL RISKS AND BENEFITS TO HUMAN PARTICIPANTS

This is a minimal risk study because of the use of marketed products and standard optometric assessments.

Contact lenses in this study will be worn on a daily wear (and daily disposable) basis. Adverse events and/ or complications in daily wear of soft contact lenses can occur (e.g. inflammation and infection). Complications that may occur during the wearing of contact lenses include discomfort, dryness, aching or itching eyes, excessive tearing, discharge, hyperemia and variable or blurred vision. More serious risks may include photophobia, iritis, corneal edema or eye infection. Although contact lens-related infections are very infrequent, the possibility does exist. The

incidence of infection due to daily-wear soft lenses is 0.035%. Almost always an infection will occur only in one eye. Thirty five million Americans who currently wear contact lenses assume this risk.

When contact lenses are worn on a daily wear basis there is a small risk of an adverse event compared to not wearing contact lenses. When contact lenses are worn on an extended wear basis, there is a significantly increased risk of an adverse reaction compared with wearing contact lenses on a daily wear basis.

A dye (fluorescein) normally used for eye exams is being used in this study. Although rare, it is possible that participants may have an allergic reaction to the dye. This could cause discomfort to their eye.

Participants are advised to inform the investigator of any sensitivities to the study products.

Parts or all of this study will be conducted during the COVID-19 pandemic. Therefore, risks exists with the infection with COVID-19. The risks of infection with COVID-19 arise due to possible exposure during commute to and from the study visit as well as during the study visit, particularly due to the closeness of the investigator and participant (within 2m for some assessments). The potential effects of COVID-19 are not yet fully known and may include long-term health consequences. In a small percentage, infection with COVID-19 can lead to serious illness, hospitalization, and in rare cases to complications leading to death. Individuals aged 60 and above and those with underlying medical conditions are considered at a greater risk for severe illness from the COVID-19 virus.

In consideration of risks associated with COVID-19, CORE has implemented a series of on-site safety procedures which have been reviewed and approved by the University of Waterloo. These include, but are not limited to, self-screening of investigators and participants prior to entering the building, maintaining physical distancing as much as possible, frequent handwashing, wearing of face masks by the investigator and participant, and frequent room and equipment hygiene and decontamination.

Participants will not benefit directly from taking part in this study.

Information from this study may help researchers come up with new soft contact lens designs to help others in the future. This study may help the study sponsor to better understand the performance of the products being used in this study in a different age cohort from that previously studied.

7 ADVERSE EVENTS

See CORE SOP012 for a description of all adverse events, including management and reporting.

Any observations taking place prior to determining that a subject meets all inclusion/ exclusion criteria for the study and which are not related to the performed study procedures are not considered an AE. An AE can be any unfavourable and unintended sign, symptom, or disease temporarily associated with a study procedure, whether there is a causal relationship or not.

Adverse events (AE) may be classified as 'unanticipated adverse device effects,' 'serious adverse events,' 'significant adverse events,' or 'non-significant adverse events,' as defined below, Table 4.

A number of conditions may result in temporary suspension until resolution. These include corneal infiltrates, corneal staining, limbal injection, bulbar injection or tarsal conjunctival abnormalities.

Table 4: Classification of types of adverse event

Classification	Definition
Serious Adverse Event	Those events that are life-threatening, or result in permanent impairment of a body function, or permanent damage to a body structure or necessitate medical (therapeutic) or surgical intervention to preclude permanent impairment of a body function or permanent damage to a body structure.
Significant Adverse Event	Those non-serious adverse events that occur with contact lens usage that are not sight-threatening but are usually symptomatic and may warrant therapeutic management and /or temporary or permanent discontinuation of contact lens wear.
Non-Significant Adverse Events	Those less severe non-serious adverse events that occur with contact lens usage that are not sight-threatening, may or may not be symptomatic and may warrant palliative management, such as ocular lubricants or temporary interruption of contact lens wear.
Unanticipated Adverse Device Effect	Adverse events in a study that were not previously identified in the protocol in terms of nature, severity, or degree of incidence. An Unanticipated Serious Adverse Device Effect is an unanticipated adverse event that is serious in nature and caused by or associated with the device and is considered reportable.

AE classification, coding (for reporting to the sponsor) and reporting details, plus examples, are provided in Table 5.

Table 5: Contact lens adverse event classification, coding and reporting guide

Code	Condition	Reporting
Serious Adverse Events		
01	Presumed infectious keratitis or infectious corneal ulcer	For all serious AEs: Notify sponsor as soon as possible, within 24 hours ; ORE reporting will be within 24 hours as per requirements
02	Permanent loss of \geq 2 lines of best spectacle corrected visual acuity (BSCVA)	
03	Corneal injury that results in permanent opacification within central cornea (6mm)	
04	Uveitis or Iritis (e.g. presence of anterior segment inflammation as described in ISO 11980, Annex B)	
05	Endophthalmitis	
06	Hyphema	
07	Hypopyon	
08	Neovascularization within the central 6mm of cornea	
00	Other serious event	
Significant Adverse Events		
11	Peripheral (outside central 6mm), non-progressive, non-infectious ulcer	Notify sponsor as soon as possible, within 5 working days ; ORE reporting as per requirements
12	Symptomatic corneal infiltrative event	
13	Superior epithelial arcuate lesions (SEALs) involving epithelial split	
14	Corneal staining \geq dense coalescent staining up to 2mm in diameter (e.g. moderate, ISO 11980 grade 3)	
15	Corneal neovascularization \geq 1.0mm vessel penetration (e.g. \geq ISO 11980 Grade 2), if 2 grade change from baseline	
16	Any temporary loss of \geq 2 lines BSCVA for \geq 2wks	
17	Any sign and/or symptom for which participant is administered therapeutic treatment or which necessitates discontinuation of lens wear for \geq 2 weeks	
10	Other significant event	
Non-significant Adverse Events		
21	Conjunctivitis (bacterial, viral or allergic)	Notify sponsor as soon as possible, within 5 working days ; ORE
22	Papillary conjunctivitis if \geq mild scattered papillae/follicles approximately 1mm in diameter (e.g. ISO 11980 Grade 2), if 2 grade change from baseline	

23	Asymptomatic corneal infiltrative events	reporting as per requirements
24	Any sign and/or symptom for which temporary lens discontinuation for > 1 day is recommended (if not already classified)	
20	Other sign and/or symptom warranting classification as a non-significant adverse event	

7.1 NORMAL OR ADAPTIVE SYMPTOMS

Transient symptoms such as end-of-day dryness, lens awareness, itching or burning or other discomfort may occur with contact lens wear and may occasionally reduce wearing time. These are not reported as adverse events unless in the investigator's opinion they are unexpected in nature, severe or have a high rate of occurrence.

7.2 PROCEDURES FOR ADVERSE EVENTS

Treatment of an adverse event will depend on its nature and severity. Based on the clinical judgment of the investigator the participant may be referred to an ophthalmologist for treatment. The investigator will attempt to determine whether the reaction is related to the test device or a result of other factors. An adverse event form will be completed for each adverse event. Whenever possible, the adverse event will be photo-documented.

Expenses incurred for medical treatment as part of study participation will be paid by the sponsor (bills and prescription receipts kept). The participant must be followed until resolution or no further change is anticipated and/or referred for further care with the appropriate health care professional and/or recorded as being under appropriate health care as per investigator's discretion. A written report will be completed indicating the subsequent treatment and resolution of the condition.

7.3 REPORTING ADVERSE EVENTS

All potential Serious and Unanticipated Adverse Device Effects that are related or possibly related to participant's participation will be reported to the Principal Investigator and the sponsor within 24 hours of the investigator becoming aware of the event. The Investigator will report the event to the University of Waterloo's Office of Research Ethics (ORE) within 24 hours of becoming aware, as

per their requirements (by fax, mail/delivery, phone, or email). All fatal or life threatening events will be reported immediately to the ORE.

Significant and Non-Significant Adverse Events will be reported to the sponsor as soon as possible, but no later than 5 working days after the occurrence. The Investigator will report the event to the ORE as per ORE requirements (by fax, mail/delivery, phone, or email).

Details of all adverse events will be included in the study report.

8 DISCONTINUATION FROM THE STUDY

Participants may be discontinued at the discretion of the investigator or sponsor in consideration of participant safety or protocol compliance, or at discretion of the participant. Participants discontinued from a study will be reimbursed \$20 per hour for their active involvement in the study (including the initial screening visit). Upon discontinuing, a participant will be offered the option of their data being withdrawn from future statistical analysis. The following is a list of possible reasons for discontinuation from the study:

- Screening failure: Participants will be discontinued if they do not meet the inclusion and exclusion criteria outlined in section 4.2.2.
- Unacceptable performance with products to be used in study: Participants may be discontinued if they are unable to achieve acceptable comfort and /or vision with the study products.
- Positive slit lamp finding: Participants may be permanently discontinued from the study depending on the severity of the condition and on the judgement of the investigator.

- Adverse event: If a participant experiences an adverse event during the study they may be discontinued based on the clinical judgement of the investigator.
- Symptoms: If the participant has persistent symptoms they may be discontinued based on the clinical judgement of the investigator.
- Disinterest, relocation or illness: The participant may choose to discontinue due to reasons within or beyond their control.
- Violation of protocol or non-compliance: The participant will be discontinued if they are unable or unwilling to follow the protocol specified visit schedules and/or study procedures.
- Instillation of topical ocular medication: The participant will be discontinued if they elect to use a topical ocular medication during the study unless that topical ocular medication is prescribed for a limited duration (less than two weeks) to treat a transient condition; in this case the participant may remain an active participant (at the discretion of the investigator) after stopping topical ocular medication following resolution of the ocular condition).
- Lost to follow-up: The participant will be discontinued if they cannot be contacted and do not return for a final exit visit, and if the investigator has made a reasonable effort to contact the participant for a final study visit.
- Premature termination of the study by the sponsor, CORE or the Office of Research Ethics at the University of Waterloo.

A discontinuation form , stating the reason for discontinuation will be completed, which requires the signatures of both the participant and the investigator except where the participant is lost to follow-up in which case only the signature of the investigator is required.

All discontinuations including their reasons will be included in the final report.

9 STUDY COMPLETION AND REMUNERATION

At the last scheduled protocol visit a study completion form will be completed, which requires the signatures of both the participant and the investigator.

Once their involvement in the study is complete, participants will be informed about receiving feedback following study completion in the Letter of Appreciation.

10 STATISTICAL ANALYSIS AND DATA MANAGEMENT

10.1 STATISTICAL ANALYSIS

All data will be analyzed by CORE at the University of Waterloo. Data analysis will be conducted using Statistica, SPSS, or other appropriate software.

Descriptive statistics will be provided for all primary outcome variables as well as information regarding baseline variables (e.g. age, sex).

QoV and CLIQ ratings will be compared between visits using either Paired t-tests or Wilcoxon matched pairs, or using ANOVA, as applicable; statistical significance will be set at 5%. The appropriate tests will be selected based on tests of normality - non-parametric tests will be used for data not showing a normal distribution. For assessments conducted for each eye separately, the right eye will be used for analysis if there is no difference between eyes.

Additional analysis may be conducted.

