2 OBJECTIVES

The objectives of the study are:

- To measure objective and subjective visual performance, patient satisfaction and to determine if these aspects change over time as myopic young adults adapt to MiSight soft contact lenses.

Primary outcome variable:

- Subjective quality of vision (QoV)

Secondary outcome variable:

- Contact lens Impact on Quality of Life (CLIQ)

[REDACTED]

[REDACTED]

[REDACTED]

[REDACTED]

[REDACTED]

[REDACTED]

[REDACTED]

[REDACTED]

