4.2 STUDY POPULATION

4.2.1 SAMPLE SIZE CALCULATION

Using a conservative estimate for repeated measure ANOVA paradigm, with 1 group, with 3 measurements (baseline, 1 month, 2 months) and f effect size of 0.25 (cumulative probability 75%), and 1-beta 0.95, the minimum sample size is n = 43. Using an attributed drop-out rate of 10-15%, the required sample size to be dispensed will be 50 participants.

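### Section 10.1 analyses per-eye measures from the right eye on the strength of an undefined check that the eyes agree, with no fallback if they differ; only supporting per-eye measures are affected

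*Combined protocol and SAP*

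**What the plan says.** The rule is one sentence in section 10.1. For measures taken on each eye, "the right eye will be used for analysis if there is no difference between eyes". Nothing else in the document says how agreement between eyes is judged, whether the check is made once or at each visit, or what is analysed when it fails.

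Other sections fix the scope of the rule:

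- Section 2 names QoV as the primary outcome and CLIQ as the secondary outcome. Both are questionnaires answered by the participant, not measured per eye. The objective is wider, however: "To measure objective and subjective visual performance, patient satisfaction".
- Section 4.3.1 has the lenses worn in both eyes. Sections 4.4.2 and 4.4.8 record acuity both monocularly and binocularly. Section 4.5.6 grades redness, staining and lid signs in fine steps (mostly 0.1 to 0.5 of a grade).
- Over-refraction is described as monocular at the fitting in section 4.4.2. For the follow-up visits the text does not say, though per eye is the natural reading.
- Sections 7.2 and 7.3 require a form for every adverse event and details of all of them in the report, with no limit to one eye.

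**The concern.** A conditional rule of this kind has three weaknesses.

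1. It treats failure to find a difference as evidence that there is none. In a study of this size that inference is weak.
2. It has only one branch. If the eyes differ, the analyst must choose between left, right, both or the mean after seeing the data, and two analysts following the same text could report different results.
3. A comparison of group means is blind to one-sided signs. If unilateral staining or redness falls equally often on either side, the mean difference is near zero, the check passes, and the left-eye cases then leave the analysed results.

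At stake are the precision and reproducibility of the objective, per-eye part of the study's objective, and the completeness of any analysed slit-lamp results.

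**Working it through.** **The plan's own figure.** Section 4.2.1 specifies a repeated-measures ANOVA "with 1 group, with 3 measurements (baseline, 1 month, 2 months) and f effect size of 0.25", "and 1-beta 0.95, the minimum sample size is n = 43". Taking alpha as 0.05 (section 10.1) and assuming a correlation of 0.5 between repeated measures and sphericity, neither of which is stated:

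- noncentrality = f² × N × m / (1 − ρ) = 0.0625 × 43 × 3 / 0.5 = 16.1, on 2 and 84 degrees of freedom;
- power = 0.951 at N = 43 and 0.947 at N = 42.

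So 43 reproduces. For drop-out, 43/0.90 rounds up to 48 and 43/0.85 to 51, and the planned 50 lies between them. These are counts of participants for a participant-level outcome, so the eye rule does not enter.

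**What a non-significant check shows.** The plan names no test. Assume a paired, two-sided 5% t-test on 43 completers. Its noncentrality is d√43, where d is the mean right-left difference divided by the standard deviation of that difference; for d = 0.3 it is 0.3 × 6.56 = 1.97.

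| Standardised difference d | Power |
|---|---|
| 0.2 | 25% |
| 0.3 | 48% |
| 0.4 | 73% |
| 0.5 | 89% |

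Power of 80% needs d of about 0.44. Real differences smaller than that would often pass as agreement.

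**What one eye costs in information.** Let both eyes have variance σ² and between-eye correlation r. One eye has variance σ², and the two-eye mean has σ²(1 + r)/2. The share of information lost by using one eye is therefore 1 − (1 + r)/2 = (1 − r)/2, and the standard error with both eyes is √((1 + r)/2) of the one-eye value. The document gives no r, so a range is shown.

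| Assumed r | Information lost with one eye | Standard error lower with both eyes |
|---|---|---|
| 0.5 | 25% | 13% |
| 0.7 | 15% | 8% |
| 0.8 | 10% | 5% |
| 0.9 | 5% | 3% |

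Here r is the correlation of the quantity analysed. For a change between visits it is the correlation of the two eyes' changes.

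**One-sided signs.** Suppose, for illustration, that 5% to 10% of 43 participants have a sign in one eye only, with either side equally likely. That is 2.15 to 4.3 participants, of whom about 1.1 to 2.15 have it in the left eye. The expected mean difference between eyes is zero, so the check gives no warning. Table 5 would not necessarily pick these up as adverse events: staining is listed from about ISO grade 3 (code 14), neovascularization and papillary change need a two-grade change (codes 15 and 22), and the residual categories (codes 10 and 20) depend on judgement. Lower left-eye grades can therefore be recorded but never analysed.

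**The case against.** The case for leaving the rule alone has real substance.

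- **One eye per participant is a valid analysis.** It avoids counting correlated eyes as independent. Pooling 86 eyes naively would understate the standard error by a factor of √(1 + r), which is 1.22 at r = 0.5 and 1.38 at r = 0.9. This stands. The fault lies in the condition and the missing fallback, and naming the right eye unconditionally would cure the data-dependence, though not the loss of precision or the left-eye gap.
- **The named outcomes are untouched.** This also stands. Section 10.1 specifies between-visit tests only for QoV and CLIQ, and promises descriptive statistics only for primary and baseline variables. It describes no slit-lamp analysis, so the point concerns whatever per-eye results are produced. Some outcomes and procedures are redacted, so the affected measures cannot be counted.

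A reader might also infer stronger things that the document does not support:

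- *Half the data are discarded.* That is true of the number of readings. Half the information is lost only if the two eyes are uncorrelated.
- *Left-eye infections would be missed.* Section 6 does say "Almost always an infection will occur only in one eye", but infectious keratitis is a serious adverse event (Table 5, code 01) and is reported whichever eye it affects. Only grades below the adverse-event thresholds are exposed.
- *The undefined branch would be reached by chance about 19% of the time per measure.* The figure is 1 − 0.95⁴, which needs a 5% eye test repeated independently at four visits. The plan states no such test and no such repetition. Visits on the same participants are unlikely to be independent, and Table 3 schedules spherical over-refraction at only two visits.

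**Conclusion.** The point holds for supporting per-eye measures only. The rule is data-dependent, its criterion is undefined, and it has no action for eyes that differ. Under the assumed paired 5% test, passing the check with 43 completers is weak evidence of agreement (48% power at a standardised difference of 0.3), and a comparison of means cannot reveal one-sided signs.

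The precision cost is modest: 25% to 5% of the information for an assumed r of 0.5 to 0.9, with equal variances in the two eyes. The left-eye gap is confined to grades that do not qualify as adverse events. The primary and secondary outcomes and the target of 43 completers do not depend on the rule, and binocular acuity offers a measure of objective vision that needs no choice of eye. The reason to act is that the ambiguity is easily removed and the data needed are already planned.

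**What to change.** Replace the conditional sentence in section 10.1 with a rule fixed in advance:

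1. Analyse continuous per-eye measures as the participant's two-eye mean, or in a mixed model with a participant random effect and eye nested within participant. Either respects the between-eye correlation, and the choice should be named in advance.
2. Report graded slit-lamp signs for right and left eyes. A worse-eye summary per participant may be added, but should not replace them: it is higher by construction, and the eye it refers to can change between visits.
3. State that QoV, CLIQ and binocular acuity are participant-level measures to which no eye rule applies.

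The cost is a few lines of text and slightly more analysis and tabulation. No new measurements are needed, on the natural reading that both lens-wearing eyes are examined at each in-office visit. The sample size does not change.
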